13.1.4.3 Secondary Analyses

Secondary and exploratory efficacy endpoints will be analyzed separately for each period (Double-blind and OLE) using descriptive statistics.

Additionally, for the Double-blind Period only, change from Baseline in continuous secondary endpoints through Week 12 will be presented and analyzed using a mixed model for repeated measures (MMRM). The model will include the change from baseline score as the dependent variable, treatment group as a fixed effect, subject as a random effect, and baseline score value as a covariate.

For subjects who report having fissures, descriptive summaries of the number of fissures and pain related to fissures will also be presented by treatment group and body area for each period.

The DLQI scores will also be analyzed using descriptive statistics through Week 12.

The proportion of subjects with at least a 50% reduction in IGA score from Baseline will be analyzed using the same logistic regression analysis described in Section [13.1.4.2](#).

13.1.4.4 Exploratory Analyses

Descriptive summaries and the changes from baseline will be provided for ectropion scores and EQ-5D-5L scores by visit for each period. No formal inferential analyses will be conducted for exploratory endpoints.

13.1.4.5 Corroborative, Sensitivity, and Other Analyses

To assess the effect of missing data on the primary efficacy analysis, a sensitivity analysis will be performed using multiple imputation (MI) for the Double-blind Period only. Multiple-imputations will be used to replace missing IGA outcomes using multiple draws from the posterior predictive

distribution estimated from the treatment groups. IGA scores will be imputed and then categorized as treatment success according to Section 13.1.4.1. Imputation will not be performed for the OLE. Full details will be specified in the SAP.

The proportion of subjects who experience a 2-grade change from baseline to Week 12 in individual score for roughness and palm/sole assessment will also be explored using a logistic regression model with treatment and age group as factors. Other baseline characteristics and interactions may be included. The odds ratios and 95% CIs for the odds ratios will be presented. The difference in proportions between the active trifarotene cream HEI and vehicle cream group and the 95% CIs for the differences will be presented.

For analyses involving study site, if the number of subjects per site is small, sites may be pooled for safety and efficacy analysis or omitted from statistical models as the anticipated number of subjects per site is small, treatment is self-administered, and the sites are using standardized procedures for all assessments. If the distribution of enrollments at sites is such that one or few are enrolling a majority of subjects, a subgroup analysis by site may be performed. The final determination will be made prior to database lock.

Details of these analyses will be further detailed in the SAP.

13.1.5 Clinical Pharmacology Analyses

13.1.5.1 Pharmacokinetics

For noncompartmental analysis, plasma concentrations will be listed and summarized at each time point using descriptive statistics. Descriptive statistics reported will include the arithmetic mean, SD, CV%, geometric mean, minimum, maximum, and median. Only the range and the median will be reported for T_{max} , as this is a categorical parameter. The PK parameters will also be summarized by treatment using descriptive statistics.

Individual plasma concentration plots and mean data graphs will be produced using both linear and semi-logarithmic scales. Mean data graphs will show plasma concentration profiles by treatment group.

Pharmacokinetic plasma parameter estimates and summaries will be completed for the subjects in the PK population. Testing of PK parameters will be outlined in the SAP.

13.1.6 Safety and Tolerability Analyses

Safety analyses through Week 12 of the Double-blind Period will be conducted using data from the Safety Population and safety analyses in the OLE will be conducted using the OLE Safety Population (as defined in Section 13.1.1). Safety variables include treatment-emergent AEs, clinical laboratory values, vital signs, ECG readings, and physical examination results. No formal inferential analyses will be conducted for safety variables in either period.

13.1.6.1 Local Tolerability

During all clinic visits, the investigator will assess local tolerability (Scale: 0-3 [none, mild, moderate, severe]) for each treated body area (chest/abdomen, back, arms, legs, and face/neck). Descriptive summaries will be presented by period, treatment group, and visit.

13.1.6.2 Adverse Events

All AEs will be coded using the Medical Dictionary for Regulatory Activities (MedDRA), Version 20.1 or higher.

Treatment-emergent AEs are defined as:

- AEs with onset at the time of or following the start of treatment with IP through the Follow-up Visit or Early Termination Visit, whichever occurs first, or
- AEs starting prior to the start of treatment but increasing in severity or relationship at the time of, or following, the start of treatment with IP through the Follow-up Visit or Early Termination Visit, whichever occurs first.

The number and percentage of subjects with AEs will be displayed by each treatment group in the Double-blind Period and overall in the OLE by system organ class and preferred term. Summaries of AEs by severity and relationship to IP will also be provided. Serious adverse events and AEs resulting in discontinuation of IP will be summarized separately in a similar manner. Subject listings of AEs, SAEs, and AEs causing discontinuation of IP will be produced.

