6.2. Secondary Objectives

The secondary objectives are as follows:

- To assess systemic exposure to trifarotene and its major metabolites after topical application of the investigational product (IP) on up to 90% BSA twice weekly.
- To assess safety for up to 24 weeks of dosing with open-label trifarotene cream HE1 200 µg/g.

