8.3. Premature Subject Withdrawal

All subjects will be advised that they are free to withdraw from participation in this study at any time, for any reason, and without prejudice. The investigator should make every reasonable attempt to keep subjects in the study; however, subjects must be withdrawn from the study if they withdraw consent to participate. Investigators must attempt to contact subjects who fail to attend scheduled visits by telephone or other means to exclude the possibility of an AE being the cause of withdrawal. Should this be the cause, the AE must be documented, reported, and followed as described in Section 11.2.

The sponsor reserves the right to request the withdrawal of a subject due to protocol deviations or other reasons.

The investigator also has the right to withdraw subjects from the study at any time for lack of therapeutic effect that is intolerable or otherwise unacceptable to the subject, for intolerable or unacceptable AEs, intercurrent illness, noncompliance with study procedures, administrative reasons, or in the investigator's opinion, to protect the subject's best interest.

If a subject is withdrawn before completing the study, the reason for withdrawal and the date of discontinuation will be recorded on the appropriate page of the electronic case report form (eCRF). Whenever possible and reasonable, the evaluations that were to be conducted at the completion of the study should be performed at the time of premature discontinuation.

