11.1.6 Treatment-Emergent Adverse Events

An AE is defined as treatment emergent if the first onset or worsening is after the first application of IP (trifarotene or vehicle) and not more than 14 days after the last application of IP.

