11.2. Event Assessment and Follow-up of Adverse Events

The occurrence of an AE or SAE may come to the attention of study personnel during study visits and interviews of a study participant presenting for medical care or upon review by a study monitor.

All reported AEs, including local and systemic AEs not meeting the criteria for SAEs, will be captured on the appropriate eCRF. Information to be collected includes event description, time of onset, clinician's assessment of severity, relationship to study product (assessed only by those with the training and authority to make a diagnosis), and time of resolution/stabilization of the event. All reported AEs occurring while on study must be documented appropriately regardless of relationship. All reported AEs will be followed to adequate resolution.

Any medical condition that is present at the time that the participant is screened will be considered as baseline and not reported as an AE. However, if the study participant's condition deteriorates at any time during the study, it will be recorded as an AE.

Changes in the severity of a reported AE will be documented to allow an assessment of the duration of the event at each level of severity to be performed. AEs characterized as intermittent require documentation of onset and duration of each episode.

Study clinic personnel will record all reportable events with start dates occurring any time after informed consent is obtained until 14 (for nonserious AEs) or 30 days (for SAEs) after the last day of study participation. At each study visit, the investigator will inquire about the occurrence of AE/SAEs since the last visit. Events will be followed for outcome information until resolution or stabilization.

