11.3. Special Considerations

11.3.1 Adverse Events of Special Interest

Since topical retinoids are associated with local application site AEs, particularly when beginning treatment, these events will be followed closely during the study and considered AEs of special interest (AESIs).

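### Sections 11.1.6 and 13.1.6.2 define treatment-emergent AEs differently, and the pooled open-label AE table cannot show AEs over 24 weeks on 200 µg/g

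*Protocol*

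**What the plan says.** **TEAE definition.** Protocol Section 11.1.6 counts an AE whose first onset or worsening comes after the first application "and not more than 14 days after the last application of IP". Section 13.1.6.2, which governs the tables, counts AEs from the start of treatment "through the Follow-up Visit or Early Termination Visit, whichever occurs first". It also widens the worsening rule to "AEs starting prior to the start of treatment but increasing in severity or relationship", whereas Section 11.1.6 mentions worsening only.

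**Collection and visit timing.** Section 11.2 has sites record events "until 14 (for nonserious AEs) or 30 days (for SAEs) after the last day of study participation". Under Section 8.3, the end-of-study evaluations of a withdrawn subject "should be performed at the time of premature discontinuation", where possible and reasonable.

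**OLE.** Section 13.1.6.2 says that AE counts and percentages "will be displayed by each treatment group in the Double-blind Period and overall in the OLE by system organ class and preferred term". All OLE subjects receive 200 µg/g (Section 9.6) for 12 weeks (Sections 10.1.1 and 10.2.4). Section 6.2 gives as a secondary objective "To assess safety for up to 24 weeks of dosing with open-label trifarotene cream HE1" at 200 µg/g. Section 11.3.1 makes application-site reactions AEs of special interest because topical retinoids are "associated with local application site AEs, particularly when beginning treatment".

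**The concern.** A programmer cannot follow both TEAE rules. The choice changes which events count in the subjects where tolerability matters most, those who stop early, and safety against vehicle over 12 weeks is part of the primary objective.

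The OLE table is a separate matter. By the protocol's own account, application-site reactions cluster at the start of treatment. In the OLE, former vehicle subjects are starting active drug, former 100 µg/g subjects are moving to the higher concentration, and former 200 µg/g subjects have already completed 12 weeks on it. One pooled percentage is neither a first-exposure rate nor a continued-exposure rate. Yet Sections 5.2 and 7.3 say that the OLE is there to evaluate the long-term safety of the higher dose.

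**Working it through.** **1. The plan's own figures.** Section 13.2 has 120 subjects randomized 1:1:1 with a 20% drop-out/nonevaluable rate: 120 × 0.80 / 3 = 32 per arm, as stated. The maximum duration also reproduces: 35 + 180 + 14 = 229 days.

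**2. The two windows in days.** Let the ET visit fall *k* days after the last application. Section 11.1.6 closes the window at day 14 and Section 13.1.6.2 at day *k*, so the difference is 14 − *k*. The protocol does not give *k*; the values below are assumed.

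| ET visit, days after last application | 11.1.6 closes | 13.1.6.2 closes | Days left out by 13.1.6.2 |
|---|---|---|---|
| 1 | 14 | 1 | 13 |
| 4 | 14 | 4 | 10 |
| 7 | 14 | 7 | 7 |
| 14 | 14 | 14 | 0 |
| 21 | 14 | 21 | −7 (13.1.6.2 is longer) |

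**3. Who is affected, and in which direction.**
- *OLE completers:* the follow-up visit is 14 days after the last administration (Section 10.2.4.7), so the two end dates agree.
- *Subjects who leave the study with a prompt ET visit:* Section 13.1.6.2 is shorter. An event in the gap is collected under Section 11.2, is a TEAE under 11.1.6 and is not one under 13.1.6.2.
- *Subjects who stop treatment but stay on visits:* Section 8.4 separates stopping treatment from withdrawal, and Table 2-1 keeps Day 90 as scheduled. Section 13.1.6.2 can then run well past 14 days and be the longer window.
- *Double-blind completers who do not enter the OLE:* their only follow-up is a telephone call within 14 days after Day 90 (Section 10.2.3), so the follow-up visit named in 13.1.6.2 has no clear date.

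**4. Who can have 24 weeks on 200 µg/g.** Twelve double-blind weeks plus 12 OLE weeks make 24, at 200 µg/g only in the arm randomized to it. If all completers enter, that is 32 of 3 × 32 = 96 subjects (33%); the other 64 (67%) have 12 weeks. At an assumed uptake of 60% or 80%, it is about 19 of 58 or 26 of 77.

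**5. What pooling does.** The pooled rate is (32 × r₁ + 64 × r₂) / 96, with r₁ for continuing 200 µg/g subjects and r₂ for the others. All rates are assumed.

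| r₁ | r₂ | Pooled |
|---|---|---|
| 10% | 20% | 16.7% |
| 10% | 30% | 23.3% |
| 20% | 40% | 33.3% |
| 15% | 5% | 8.3% |

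The pooled figure describes neither group in any row.

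**6. Precision.** With zero events, the exact one-sided 95% upper bound is 1 − 0.05^(1/n): 8.9% for n = 32 and 3.1% for n = 96. Reading the pooled table as 24-week evidence would overstate its precision about threefold (8.9 / 3.1 ≈ 2.9).

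**The case against.** Several stronger readings are tempting, and the protocol does not support them.

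- *That the events are lost.* They lose TEAE status only. Section 11.2 still has them recorded, and Section 13.1.6.2 plans subject listings of AEs, SAEs and AEs causing discontinuation.
- *That anyone who stops for irritation loses up to 14 days.* The protocol asks subjects who stop treatment to stay on visits, and for them Section 13.1.6.2 may be the wider rule. That the loss concentrates in the active arms is therefore not established.
- *That about 8 subjects per arm are affected (40 × 0.20).* The 20% combines drop-outs with nonevaluable subjects and says nothing about when an ET visit takes place.
- *That the double-blind tables run on to Week 26.* Sections 13.1 and 13.1.6 separate the periods at Week 12. What is missing is an explicit rule for events around the first OLE application.
- *That the 24-week objective goes unanswered.* Local tolerability and laboratory values are summarized by treatment group and period (Sections 13.1.6.1 and 13.1.6.3), although the text does not say whether treatment group in the OLE means the prior arm.

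It can also be argued that an overall column is a normal protocol-level summary when everyone receives the same product, and that columns by prior arm belong in the SAP. That is fair as far as it goes, and a SAP may add them. But the protocol does more than stay silent: it fixes the OLE display as pooled, against its own account of when these reactions occur. OLE pooling does not touch the 12-week comparison with vehicle, which is shown by arm.

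**Conclusion.** The point holds in two limited parts.

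First, the TEAE definitions in Sections 11.1.6 and 13.1.6.2 are incompatible in end date and in worsening criterion. The size depends on when the ET visit falls: 10 to 13 days fewer under 13.1.6.2 at 1 to 4 days after the last application (assumed), none at 14 days, and the reverse beyond that. The number of subjects affected cannot be derived from the protocol.

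Second, no planned AE table answers the 24-week objective. The OLE table pools three exposure histories, and the objective attaches 24 weeks to open-label dosing that lasts 12. About 32 subjects can reach 24 weeks at 200 µg/g, given the planned 20% rate and entry of all completers. Lower uptake reduces that number; fewer dropouts could raise it towards 40. The objective is under-served by the AE tables, not wholly unanswered.

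This should be corrected, but it does not threaten the design.

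**What to change.** 1. Put one TEAE definition in both sections: onset or worsening from the first application to 14 days after the last, with AEs starting at or after the first OLE application assigned to the OLE. State one worsening criterion, and say whether a change in relationship alone qualifies. A window tied to the last application also removes the need for a follow-up visit date in subjects who do not enter the OLE.
2. Show OLE AEs by prior arm (vehicle, 100 µg/g, 200 µg/g) plus total.
3. Add a 0–24 week AE summary for subjects on 200 µg/g in both periods.
4. Reword the Section 6.2 objective to say up to 24 weeks in subjects randomized to 200 µg/g and up to 12 weeks in the others.

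The cost is wording in three sections, extra table columns and one extra summary. No new data are needed, and neither visits nor sample size change.

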13.1.6.3 Clinical Laboratory Evaluations

Descriptive summaries (mean, SD, median, minimum, and maximum) of actual (absolute) values and changes from baseline values will be presented for clinical laboratory values for each treatment group at each time point in each period.

The number of subjects with clinical laboratory values categorized as below, within, or above normal ranges will be tabulated showing change from baseline (shift tables) for each clinical laboratory parameter by treatment group and by study visit in each period.

Laboratory values that are outside the normal range will also be flagged in the data listings and presented with the corresponding normal ranges. Any out-of-range values that are identified by the investigator as being clinically significant will also be shown in a data listing.

13.1.6.4 Vital Signs

Descriptive summaries (mean, SD, median, minimum, and maximum) of actual values and changes from baseline will be calculated for systolic blood pressure (SBP), diastolic blood pressure (DBP), and pulse for each period.

The number of subjects with vital signs values categorized as below, within, or above normal ranges will be tabulated showing change from baseline (shift tables) for each parameter by period, by treatment group and by study visit. Pre and post-treatment values may also be presented with an analysis of mean changes from baseline.

13.1.6.5 Twelve-lead Electrocardiograms

The number and percentage of subjects with normal and abnormal ECG findings will be summarized for each treatment group at each time point in each period. Abnormal results will be grouped as clinically significant and not clinically significant.

A comparison of QT results will be presented. Summary statistics will be displayed by period, by treatment group, and by visit for QT and the QT interval corrected for heart rate (QTc) calculated using Fridericia's QT correction methods.

Descriptive summaries (mean, SD, median, minimum, and maximum) will be presented for ECG measures of PR interval, QRS interval, QT interval, QTcF interval (Fridericia's correction methods), and HR for each treatment group at each time point in each period.

13.1.6.6 Physical Examination Findings

The number and percentage of subjects with normal and abnormal findings in the complete physical examination will be displayed for each treatment group in each period.

13.1.7 Interim Analysis

No interim analyses are planned.

13.2. Sample Size Determination

Accounting for a 20% drop-out/nonevaluable rate, a total sample size of 120 subjects randomized in a 1:1:1 ratio to 2 active trifarotene cream HE1 arms and a vehicle cream arm will provide >80% power to detect a difference between each separate trifarotene cream HE1 arm (32 evaluable subjects) and the vehicle cream arm (32 evaluable subjects) 2-sided Fisher's Exact Test assuming a 70% success rate and a 40% success rate, respectively. This study is not powered to detect a difference between the 2 active arms.

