13. STATISTICS

13.1. Statistical Analysis

This section presents a summary of the planned statistical analyses. A SAP that describes the details of the analyses to be conducted will be written prior to database lock.

Unless otherwise indicated, all testing of statistical significance will be two-sided, and a difference resulting in a P value of ≤ 0.05 will be considered statistically significant.

Summary statistics will be provided for the variables described below. For continuous variables, these statistics will include the number of subjects, mean, standard deviation (SD), median, minimum, and maximum. For categorical variables, these statistics will include the number and percentage of subjects in each category.

The primary analysis period is the first 12 weeks of treatment (i.e., the Double-blind Period). Overall unblinding will take place at the end of the Double-blind Period of the study only after the database is locked. A second analysis will take place for endpoints assessed from Week 12 through the OLE Period. The baseline for the safety and efficacy parameters will be measured at Visit 1 or Visit 2, per the Schedule of Events for both the Double-blind Period (Table 2-1) and OLE (Table 2-2).

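### The sample size section claims more than 80% power, but its own inputs give about 62%

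*Protocol*

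**What the plan says.** Section 13.2 (Sample Size Determination) opens with "Accounting for a 20% drop-out/nonevaluable rate" and plans "a total sample size of 120 subjects randomized in a 1:1:1 ratio", that is, 40 per arm. It then says that this number "will provide >80% power to detect a difference between each separate trifarotene cream HE1 arm (32 evaluable subjects) and the vehicle cream arm", where the vehicle arm also has 32 evaluable subjects. The test and effect are given as a "2-sided Fisher's Exact Test assuming a 70% success rate and a 40% success rate, respectively". The Sample Size Determination row of the Synopsis repeats the statement.

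Section 13.1 supplies the significance level: "all testing of statistical significance will be two-sided", and "a difference resulting in a P value of ≤ 0.05 will be considered statistically significant".

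Two other provisions matter for the reading. Section 13.1.4.2 makes the primary analysis a logistic regression with treatment and age group as factors. Section 13.1.1 names the ITT population, all randomized subjects, as the primary efficacy population.

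**The concern.** A 30-point difference between proportions near the middle of the scale, with 32 per arm, is a modest design for an exact test. A power above 80% looked too high on sight.

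This is the only quantitative justification for the size of the trial on its primary endpoint. If the figure is wrong, anyone weighing the design, or later interpreting a dose that fails to separate from vehicle, works with a type II risk that is understated by about half. Sections 5.2 and 7.3 say that the study is meant to determine which of the two doses is most effective, so a non-significant arm could be read as evidence against that dose when the comparison was underpowered for the effect the sponsor assumes.

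**Working it through.** **Inputs, all from the protocol**

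- Evaluable subjects: 32 per arm (Section 13.2)
- Success rates: 70% active, 40% vehicle (Section 13.2)
- Test: two-sided Fisher's exact (Section 13.2)
- Significance level: 0.05, two-sided (Section 13.1)
- Losses: 20% (Section 13.2)

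**Step 1: the dropout arithmetic.** 32 / (1 − 0.20) = 40 per arm, and 3 × 40 = 120. This part is right.

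**Step 2: the stated power.** For X ~ Bin(n, 0.70) and Y ~ Bin(n, 0.40),

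power = Σ P(X = i) · P(Y = j), summed over all tables (i, j) with two-sided Fisher p ≤ 0.05.

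| Evaluable per arm | Power |
|---|---|
| 32 | 61.9% |
| 40 | 72.5% |
| 47 | 78.6% |
| 48 | 80.05% |
| 49 | 81.5% |

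The claim of more than 80% is not reproduced. At 32 per arm the shortfall is about 18 points, and the type II risk is 100 − 61.9 = 38.1% rather than under 20%. With 20% losses, 48 evaluable per arm would mean 48 / 0.8 = 60 randomized per arm, 180 in total.

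**Step 3: other readings of the same sentence**

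The normal approximation without continuity correction at n = 32 gives

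z = [0.30·√32 − 1.96·√(2 × 0.55 × 0.45)] / √(0.7 × 0.3 + 0.4 × 0.6) = (1.697 − 1.379) / 0.671 = 0.474,

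which is a power of 68.2%. The chi-square and logistic rows below come from the same exact enumeration with a different rejection rule.

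| Two-sided 0.05 test | 32 per arm | 40 per arm |
|---|---|---|
| Fisher's exact | 61.9% | 72.5% |
| Normal approximation | 68.2% | 78.0% |
| Pearson chi-square | 71.3% | 79.6% |
| Logistic, Wald or likelihood ratio, treatment only | 71.3% | 79.6–79.7% |

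No two-sided variant exceeds 80% at 32 or at 40 per arm. A one-sided 0.05 normal approximation at 32 per arm comes closest, at 79.0%. It also misses 80% and contradicts the stated two-sided test.

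**Step 4: what 32 per arm can detect.** With vehicle held at 40%, Fisher power is 79.7% for an active rate of 76% and 82.2% for 77%. The design therefore has 80% power for a difference of about 37 points, not 30.

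**Step 5: a likely origin (inference only).** Section 13.2 of the protocol before Amendment 1 had the same 120 subjects, the same 32 evaluable per arm and the same claim of more than 80%, for a t-test with mean difference 1.0 and SD 1.4. With d = 1 / 1.4 and n = 32 per arm, the noncentral t gives 80.3% (normal approximation 81.5%), so that claim was correct. The numbers seem to have been kept when the primary endpoint became binary. The finding does not depend on this.

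**The case against.** The strongest objection is that Fisher's test is not the primary analysis. The trial will be analysed by logistic regression in all randomized subjects. If all 40 per arm contribute an outcome and the assumed rates hold, the unadjusted logistic power is 79.6–79.7%, so the practical risk of missing the effect would be about 20%, not 38%. This point stands in part: the 38% belongs to the calculation as the protocol states it, and the risk under the planned analysis lies between about 20% and 29%, depending on how many outcomes are available and how missing ones are handled. It does not make the sentence true. The sentence names Fisher's test and 32 evaluable subjects, and even the favourable reading does not exceed 80%.

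Other limits are fair. This is a phase 2 study, its primary objective covers safety as well as efficacy, and it disclaims power between the two active arms. These soften the consequence but leave the figure unchanged. Counting the 20% lost as failures (0.8 × 70% = 56% against 0.8 × 40% = 32%, 40 per arm) would bring Fisher power to 51.3%. The protocol does not specify that rule, so this is only an illustration and carries no weight here.

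Finally, the material also contains the closing sections of another protocol version, whose Section 13 is not available. The finding is established for Amendment 1. If that other version already restates the power, the correction may exist there.

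**Conclusion.** The concern holds. On the protocol's own inputs, power for each dose against vehicle is 61.9%, about 18 points below the stated minimum of 80%. With every randomized subject evaluable it is 72.5%. The result needs no outside assumption: rates, test, level and sample size are all given in Sections 13.1 and 13.2. It applies to each comparison separately at a two-sided 0.05 level with no multiplicity adjustment. At 0.025 per comparison, Fisher power at 32 per arm would be 51.6%. The logistic figures leave out the age-group factor. Because the protocol itself states the number, a statistical analysis plan cannot put it right.

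**What to change.** Correct Section 13.2 and the matching row of the Synopsis so that they say:

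- with 32 evaluable subjects per arm, a two-sided Fisher's exact test at 0.05 has about 62% power for 70% against 40%;
- the difference detectable with 80% power at that size is about 37 points (roughly 77% against 40%);
- the logistic primary analysis, taken without the age factor, has about 71% power at 32 per arm and just under 80% if all 40 per arm have an outcome.

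Give the test, the number per arm and the missing-data assumption next to each figure.

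The cost is a wording change in two places and a less favourable headline figure. The correction does not require more subjects. If the sponsor wants to keep 80% power for 70% against 40% with Fisher's test, that is a separate decision and would need 48 evaluable per arm (180 randomized at 20% losses).
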